6.0 CRITERIA FOR PARTICIPANT ELIGIBILITY

6.1 Participant Inclusion Criteria

Caregivers

- 1) As per self-report, age 18 years or older.
- 2) As per self-report, are a current caregiver to an MSK or MGH patient with any site/stage of cancer who has received any type of treatment (e.g. curative, palliative) in the past 12 months.
- 3) Experience distress as evidenced by a score of 4 or greater on the Distress Thermometer (DT) **and** answer “Yes” to at least one of the follow-up questions (i.e.

reporting that their distress is related to their caregiving experience, **or** their distress started or is related to caregiving or has gotten worse since the patient was diagnosed or began treatment). (N/A for training case participants)

- 4) English fluent: Self-report by subject identifying English as the preferred language for healthcare, and self-reported degree of fluency as speaking English “Very well.”
- 5) As per self-report, residing in New York or New Jersey (for MSK participants), or Massachusetts (for MGH participants), or have the ability to complete sessions while complying with current telehealth regulations.

Patients

- 1) Age 18 years or older as per EMR.
- 2) Patient of an eligible caregiver, as per self-report or the EMR.
- 3) English speaking as per the EMR or self report by subject identifying English as the preferred language for healthcare, and self-reported degree of fluency as speaking English “Very well.”.

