9.0 PRE-TREATMENT/INTERVENTION

MEASURE/TEST	Time to complete	Screening ^a		Baseline (T1) ^b	
		Caregiver	Pt	Caregiver	Pt
Screening Questionnaire Packet	2 min	X	X		

Demographic Information and Psychosocial Services Use, Preferences, and Perceived Barriers	10 min			X	
Distress Thermometer (DT)	2 min	X		X	
Hospital Anxiety and Depression Scale (HADS)	5 min			X	
Penn State Worry Questionnaire	5 min			X	
Rumination-Reflection Questionnaire, Rumination subscale	5 min			X	
Attentional Control Scale	5 min			X	
Experiences Questionnaire, Decentering subscale	5 min			X	
Emotion Regulation Questionnaire, Reappraisal subscale	3 min			X	
Caregiver Quality of Life Index-Cancer	50 min			X	
Caregiver Reaction Assessment (CRA)	5 min			X	
Self-Administered Comorbidity Questionnaire (SCQ)	5 min			X	
Patient-Reported Outcomes Measurement Information System Global Health Scale (PROMIS-GH)	5 min			X	X
EORTC QLQ-C30	3 min				X
Perceived Stress Scale	4 min				X
National Survey on Drug Use and Health, Healthcare Utilization	2 min				X
Inflammatory Markers Assessment	5 min			X	
Diurnal Cortisol Assessment	2 min. 4x a day over 3 days			X	
Total Time		4 min	2 min	86 min	14 min

^a Training case participants will not be required to screen in with the measures. ^b Training case participants will not complete the Baseline assessment.

The *Distress Thermometer*¹⁵⁰ is a single-item visual analog scale widely used to screen patients with cancer and caregivers for distress¹⁵¹⁻¹⁵⁵ with a 0-10 range accompanied by a 34-item problem checklist^{156,157}. A score of 4 or greater indicates clinically significant distress^{158,159} (Appendix H).

Demographic Information and Psychosocial Services Use, Preferences, and Perceived Barriers survey was designed by adapting items from a prior study from our group¹⁶⁰. Demographic information, past/current psychosocial service use, support needs, intervention preferences, and perceived barriers are assessed through Likert-scale ratings and open-ended items (Appendix H).

*Hospital Anxiety and Depression Scale (HADS)*¹⁶¹ is a 14-item questionnaire of overall psychological distress, well-tested in cancer populations¹⁶². Developed by Zigmond and

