We will test differential effects of ERT-C versus CBT-C using separate GLIMMIX/HLM for each outcome (e.g., depression, anxiety). For HADS outcomes and for rumination and worry post-intervention outcomes, the *i*th caregiver, within the *j*th site, at the *k*th timepoint will be regressed on a time variable, an indicator for ERT-C arm, and time-by-arm interaction. That is, baseline assessments will be included as an outcome and not a covariate. This flexible analytic strategy will allow testing of non-linear time effects, treatment differences immediately post-treatment, and comparison of 6-month maintenance, all within the same model framework via specific contrasts. This strategy also utilizes all complete assessments, such that caregivers who miss data at a subset

of time points will still be included and analyzed in the model. Random per-caregiver and per-site intercepts will control for intraclass correlation introduced by repeated measures and cluster effects, which is an important statistical consideration in choosing GLIMMIX/HLM as our primary statistical approach. Prior to regression modeling, transformations to the outcome will be made as necessary and based on tests of parametric assumptions. A significant finding on the test of the interaction term would be evidence that there is a differential reduction in the outcome by treatment assignment. For immediate gains, data will be restricted to T1 to T2 (including the mid-intervention assessments for HADS outcomes). For 6-month maintenance, a similar model will be used, restricted to the post-intervention data. For HADS outcomes pre to post intervention, 10 assessments (T1, T2, and 8 mid-intervention timepoints) are expected; for all 4 primary outcomes, 3 timepoint assessments (T2, T3, T4) are expected for 6-month maintenance. A significant finding on the main time effect would indicate a change in outcomes during the 6-month follow-up for CBT-C participants, and a significant finding on the interaction coefficient would indicate a significantly different change in follow-up outcomes between ERT-C and CBT-C. Superiority is defined by a significant finding on post-treatment difference (T1 to T2) and either further significant differentiation post-intervention (T3 to T5) or no statistically significant differentiation if the CBT-C group converges with the ERT-C group during this time.

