Power and Sample Size for Aim 2. Statistical power for mediation models was estimated from simulations by Fritz and MacKinnon, [202] which provide conservative estimates given the reduction in noise provided by our weekly assessments and growth curve modeling. Allowing for up to 20% attrition, the sample will provide at least 80% power to detect mediation using the Sobel test if one of the two paths (α or β) has a small-medium effect size (Cohen's $d=0.39$), and the other has at least a small effect ($d=0.26$).

Aim 3: Differential Effects of Treatment on Change in Biomarkers. We will describe and test differential changes in inflammation and salivary biomarkers overall and by treatment arm.

Hypothesis 3a: ERT-C will result in greater reductions in cortisol dysregulation and systemic inflammation as compared to CBT-C and gains will be maintained at 6-months follow-up.

Exploratory Hypothesis 3b: Reductions in cortisol dysregulation and systemic inflammation observed with ERT-C will be most prominent in caregivers with baseline elevations in distress.

Primary Analyses: The same HLM/GLIMMIX framework from Aim 1 will be used for Aim 3. Transformations may be needed for both biomarkers. The analysis will be similarly conducted to assess both differential pre-post change (T1 to T2) and also maintenance at 6-months follow-up (T2 to T4), using appropriate contrasts on the time variable. This same framework will allow for testing the exploratory moderation hypothesis. Specifically, for Hypothesis 3b, outcomes will be regressed on the ERT-C indicator, an indicator of elevated baseline distress, and the interaction of the two. A significant finding on the interaction term will be evidence to a moderation effect and will be followed with stratified analyses of the biomarker outcomes by baseline distress category and treatment arm.

Power and Sample Size for Aim 3. Based on previous participation rates with biological samples at our institutions, we anticipate at least 75% of the 240 enrolled caregivers to provide samples. With a conservative 20% attrition assumption, an analytic sample of $n=144$ would provide 80% power to detect a small-medium effect size of $d=0.36$ for the t-test for Hypothesis 3a.

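### Exploratory Hypothesis 3b rests on a binary distress indicator with no stated measure or cut-off, and does not say whether its outcomes are change scores or repeated values

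*Combined protocol and SAP*

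**What the plan says.** Hypothesis 3b, labelled exploratory in Sections 2.0 and 14.0, reads "Reductions in cortisol dysregulation and systemic inflammation observed with ERT-C will be most prominent in caregivers with baseline elevations in distress". It is therefore a statement about change, and about how the arm difference in change varies with distress.

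The Aim 3 analysis text borrows the Aim 1 mixed-model framework, assesses T1 to T2 and T2 to T4 change "using appropriate contrasts on the time variable", and adds that "This same framework will allow for testing the exploratory moderation hypothesis". The specific model for 3b follows: "outcomes will be regressed on the ERT-C indicator, an indicator of elevated baseline distress, and the interaction of the two". A significant interaction is to be followed by analyses stratified on distress category and arm. No instrument, threshold, visit or change score is named.

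Elsewhere:
- Section 6.1, caregiver criterion 3, requires a DT score of at least 4 for entry (training cases exempt).
- Section 9.0 says of the DT: "A score of 4 or greater indicates clinically significant distress". No other distress cut-off appears in the document.
- The Section 9.0 table repeats the DT at T1 and also collects the HADS there. The HADS is described as a measure of overall psychological distress, is scored as two subscales of 0 to 21, and is not an entry criterion.
- In the Aim 1 framework each outcome "will be regressed on a time variable, an indicator for ERT-C arm, and time-by-arm interaction", and "baseline assessments will be included as an outcome and not a covariate".
- The Aim 1 moderator models use change scores explicitly, with arm, moderator and their two-way interaction.

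**The concern.** Two choices that determine the 3b test are left open.

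The first is the moderator. A reader looking for the plan's own definition of elevated distress finds only the threshold that caregivers had to meet to be enrolled. Used as the indicator, it leaves almost nobody in the comparison group. Any other threshold has to be chosen later, possibly with the data in view, and would apply to at least seven biomarker summaries: three inflammatory markers and four cortisol indices (Section 9.0). The stratified follow-up analyses inherit the same split.

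The second is the outcome. The hypothesis concerns reductions, but the model sentence has no time term and no change score, and the framework it sits in treats T1 as one of the outcome values. Two analysts following the text could fit different models and report different moderation effects.

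**Working it through.** **Inputs from the document.** 240 caregivers, 75% providing samples, 20% attrition (Section 14.0, Aim 3); 1:1 allocation (Section 7.2); DT cut-off of 4 (Sections 6.1 and 9.0).

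**Assumptions.** Two-sided alpha 0.05, since Aim 3 states none. The share q of analysed caregivers classed as elevated is not stated, so a range of 0.50 to 1.00 is shown. Effects are in SD units of the biomarker change score.

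**1. The plan's own figure.** 240 × 0.75 × 0.80 = 144, which reproduces. The plan gives no power or effect size for 3b. Its claim of 80% power for d = 0.36 belongs to 3a. That claim does not reproduce at n = 144 with a two-sample t-test (57% two-sided, 69% one-sided), but this is a separate matter and nothing below uses it.

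**2. The indicator at the entry cut-off.** If every analysed caregiver is elevated, the indicator column equals the intercept and the interaction column equals the arm column. The design matrix has rank 2 of 4, so the interaction cannot be estimated. If a few fall below 4 at T1:

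SE = √[4/(Nq) + 4/(N(1 − q))], and the interaction detectable with 80% power = (1.960 + 0.842) × SE, with N = 144.

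| q elevated | Non-elevated per arm | SE | Detectable interaction (SD) |
|---|---|---|---|
| 0.50 | 36.0 | 0.333 | 0.93 |
| 0.75 | 18.0 | 0.385 | 1.08 |
| 0.90 | 7.2 | 0.556 | 1.56 |
| 0.95 | 3.6 | 0.765 | 2.14 |
| 1.00 | 0 | – | not estimable |

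**3. The cost of a higher cut.** For a normal moderator with a linear effect, cutting at quantile p keeps the fraction φ(z)²/[p(1 − p)] of the information.
- Median split: 0.637, a loss of about 36%; 144 × 0.637 ≈ 92 caregivers' worth.
- 70/30 split: 0.576.
- 80/20 split: 0.490.

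**4. The missing time term.** Let the true interaction on T1–T2 change be δ. At T1, before treatment, the expected arm-by-distress interaction is 0; at T2 it is δ. A model without time that pools both visits therefore estimates (0 + δ)/2 = δ/2. If all four visits were pooled and the effect stayed constant after T2, it would estimate (0 + 3δ)/4 = 0.75δ.

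A simulation (N = 144, half elevated, within-person correlation 0.5, unit variance at each visit, δ = −1.0, 4,000 runs) gave:

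| Outcome in the arm × distress model | Mean coefficient | Power |
|---|---|---|
| T1 and T2 pooled, no time term | −0.50 | 40% |
| T2 values only | −1.00 | 85% |
| T1–T2 change score | −1.00 | 85% |

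With two complete visits, the change-score interaction is the same quantity as the arm × time × distress term.

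**The case against.** A reader might infer that 3b cannot test differential reduction at all. The documents do not support that. The sentence just before the model places 3b in a framework that has time and time contrasts, and the Aim 1 moderator models use the same two-way form on change scores, where it is the correct test. Under randomisation, T2 values alone also give an unbiased interaction. Only a literal fit that pools T1 with later visits goes wrong, and it dilutes the effect without removing it. The absence of a baseline-biomarker covariate is not a defect either, because the framework deliberately treats baseline as an outcome.

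A reader might also infer that the entry criterion by itself defeats the moderator. It does not. The plan never says that elevated means DT of 4 or more. A higher DT cut, a HADS cut or a median split would vary among enrolled caregivers, DT at T1 can differ from DT at screening, and the planned stratified analyses presuppose more than one populated category.

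Finally, the information-loss figures are general results that assume normality and linearity, neither of which the documents establish. If the moderation were a true step at a known threshold, a binary indicator there would lose nothing.

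These points stand and limit the criticism. They do not supply the measure, the cut-off or the form of the outcome, and the document gives no reason to expect a step. Section 3.0 cites a meta-analysis in which the CRP effect was stronger at higher pretreatment distress, which a continuous score can represent directly.

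**Conclusion.** The point holds as a gap in specification and an inefficient choice of moderator. Neither the indicator nor the outcome form is defined. If the only documented cut-off is used, the interaction is inestimable, or detectable only at about 1.6 to 2.1 SD with 90% to 95% of caregivers elevated. An even split brings this to 0.93 SD, but a median split gives up about 36% of the information under the normal, linear assumption. Fitting T1 and T2 together without time would halve the moderation effect. These figures assume n = 144, two-sided alpha 0.05 and the stated range for q; the simulated power also assumes a correlation of 0.5.

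Severity is low: 3b is exploratory, carries no power claim, and touches neither the primary outcomes nor Hypothesis 3a.

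**What to change.** In the Aim 3 analysis text, replace the indicator with a named continuous distress score from T1. The sum of the two HADS subscales is one candidate; the DT score is another, though its range is restricted by the entry rule. If the HADS sum is used, say so, because Section 9.0 describes only the subscale scores.

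State the test as arm × distress on biomarker change scores, or equivalently arm × time × distress in the Aim 3 mixed model, and name the contrast (T1 to T2, and T2 to T4 if maintenance is also of interest).

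Report predicted arm effects with confidence intervals at the 25th and 75th percentiles of baseline distress, in place of or beside the stratified analyses. If a binary indicator is kept, name its measure and a cut-off above the entry level before the data are seen.

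The cost is a sentence or two in the plan and no new data. The downside is an assumption that moderation is linear in distress, which can be checked, for example with a quadratic term or a plot.

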7.2 Randomization

Participants will be randomized upon registration in CTMS through MSKCC CRDB. Randomization will be 1:1 into ERT-C or CBT-C, stratified by site (i.e., MSK or MGH), using randomly permuted blocks of random length. MSK will provide randomization for both MSK and MGH. MSK will email MGH research staff the randomization results once they are assigned. Training case participants will get assigned to an arm (rather than randomized) based on the needs of our interventionist trainings. MGH participants will be registered in both MSK CTMS and MGH OnCore per MGH policy.

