Power and Sample Size for Aim 1. Preliminary data found ERT-C to have a pre-treatment to post-treatment effect size of $g=0.49$ on depression and anxiety. A recent meta-analysis found very small ($g=0.08$) effects of CBT on these outcomes; this implicates a differential effect size of $d=0.41$. Using an HLM model with up to 3 time points, a within-subject ICC of 0.2, allowing for approximately 20% attrition, and setting Type I error to the conservative value of 0.0125 to account for 4 primary outcomes, we simulate 90.4% power for the differential pre-treatment to post-treatment changes for Aim 1 if the effect size is at least $g=0.41$ and 82.8% power for a more conservative effect of $g=0.37$. Power was simulated using the *simr* [199] package in R. For patient outcomes, the PI anticipates at least 50% enrollment of patients associated to the caregivers, and comparable attrition between patients and caregivers. Enrollment of 120 patients, with 80% retention at the 3-month follow-up assessment will provide 80% power to detect a standardized effect of at least $d=0.63$ for the difference in change scores using an independent samples t-test approximation at alpha of 0.05. Similarly for rumination and worry from pre to post intervention, enrollment of 240 caregivers with 10% attrition during intervention will provide 80% power to detect a medium effect of at least $d=0.50$ with alpha of 0.0125 for these two primary outcomes.

AIM 2: Attention and Metacognitive Regulation Will Have Indirect Effects on the Primary and Secondary Outcomes. Growth curve models will assess overall effects of treatment on primary and secondary outcomes, and the partial mediation of primary outcomes via attention and metacognition regulation skills increases and whether this effect will be more pronounced in ERT-C compared to CBT-C.

Hypothesis 2a: Only skills that specifically target components of distress (i.e., attention regulation, metacognitive regulation) will mediate primary and secondary caregiver outcomes compared to other facets of improving the caregiving experience (i.e., reducing perceived burden, maladaptive behavioral coping).

Hypothesis 2b: These gains and mediation in attention and metacognitive regulation will be more pronounced in caregivers receiving ERT-C as compared to CBT-C.

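### The Aim 3 power statement is wrong as written: 144 caregivers give 80% power for d=0.47, and about 57% power at the stated d=0.36 (two-sided alpha 0.05 assumed)

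*Combined protocol and SAP*

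**What the plan says.** The statement is in Section 14.0, under Power and Sample Size for Aim 3. The plan starts from biospecimen participation: "we anticipate at least 75% of the 240 enrolled caregivers to provide samples". It then takes a further loss ("With a conservative 20% attrition assumption") and concludes that "an analytic sample of $n=144$ would provide 80% power to detect a small-medium effect size of $d=0.36$ for the t-test". The test is named as being "for the t-test for Hypothesis 3a", and that hypothesis is a comparison between arms: "ERT-C will result in greater reductions in cortisol dysregulation and systemic inflammation as compared to CBT-C". Section 7.2 fixes the allocation: "Randomization will be 1:1 into ERT-C or CBT-C". The Aim 3 paragraph gives no alpha, no sidedness, no correlation between timepoints and no other variance reduction.

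The Aim 1 power paragraph in the same section has two statements of the same kind. For patient outcomes: "Enrollment of 120 patients, with 80% retention at the 3-month follow-up assessment will provide 80% power to detect a standardized effect" of at least d=0.63, by an independent-samples t-test approximation at alpha 0.05. For worry and rumination from pre to post: "enrollment of 240 caregivers with 10% attrition during intervention will provide 80% power to detect a medium effect" of at least d=0.50 at alpha 0.0125.

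**The concern.** An effect near 0.36 at 80% power normally calls for roughly 240 analysed participants in a two-arm t-test. The plan claims it with 144. If the claim is wrong, the chance of missing a true effect of the stated size is about 43%, against the 20% that the plan implies. Hypothesis 3a is a stated hypothesis; only 3b is labelled exploratory. Readers will use the stated power to judge what a non-significant biomarker result can exclude, and on the present text they would credit the comparison with more sensitivity than it has.

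**Working it through.** **Inputs.** 240 caregivers, 75% giving samples and 20% attrition (Section 14.0, Aim 3); 1:1 allocation (Section 7.2); a two-sample t-test, because Hypothesis 3a compares the arms. Alpha is assumed two-sided 0.05, with alternatives below. Results use the noncentral t distribution; the normal approximation is shown so that they can be checked by hand.

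**Sample size.** 240 x 0.75 = 180; 180 x 0.80 = 144; 72 per arm. This reproduces the plan's n.

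**Power at d=0.36.** The noncentrality is d x sqrt(n per arm / 2) = 0.36 x sqrt(36) = 2.16. Normal approximation: Phi(2.16 - 1.96) = Phi(0.20) = 57.9%. Noncentral t: 57.4%. The stated 80% does not reproduce; the gap is about 23 percentage points.

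**Detectable effect at 80% power.** (1.960 + 0.842) / 6 = 0.467 by the normal approximation; 0.470 by the noncentral t.

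**Sample size needed for d=0.36.** 2 x (2.802 / 0.36)^2 = 121.1, so 122 per arm (244) by the normal approximation; 123 per arm (246) by the t. Either total exceeds the 240 enrolled before any loss.

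**Other choices of alpha, 72 per arm:**

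| Alpha | d at 80% power | Power at d=0.36 |
|---|---|---|
| two-sided 0.05 | 0.470 | 57% |
| one-sided 0.05 | 0.416 | 69% |
| two-sided 0.0125 (the Aim 1 level) | 0.563 | 36% |
| one-sided 0.10 | 0.355 | 81% |

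Only the last row reaches the stated figure, and nothing in the plan supports that alpha.

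**Where 0.36 does appear.** All 240 caregivers at two-sided 0.05 give d=0.363 (power at 0.36: 79.3%). A sample of 192 (240 x 0.80) at one-sided 0.05 gives d=0.360. Neither is the stated n. A one-sample or paired test gives 0.235 (n=144) or 0.335 (n=72), and would not test a between-arm hypothesis.

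**The two Aim 1 figures (two-sided assumed).**

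- Patients: 120 x 0.80 = 96, 48 per arm. The detectable effect is 2.802 / sqrt(24) = 0.572 (t: 0.578), against 0.63 stated. Power at 0.63 is 86%.
- Worry and rumination: 240 x 0.90 = 216, 108 per arm, alpha 0.0125. The detectable effect is (2.498 + 0.842) / sqrt(54) = 0.455 (t: 0.458), against 0.50 stated. Power at 0.50 is 87.5%.

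**The case against.** The best defence is that the planned analysis is a mixed model on repeated measurements, and that d may be meant in units of the raw-score standard deviation. With 144 analysed, 80% power at 0.36 would then need a baseline to follow-up correlation of about 0.71 for change scores (0.36/0.470 = 0.766; 1 - 0.766^2/2 = 0.71), or about 0.64 with baseline adjustment (sqrt(1 - 0.766^2) = 0.64). This shows that 0.36 is not impossible under some analysis. It does not rescue the text: the power is claimed for the t-test, and no biomarker correlation is given. The only within-subject correlation stated in Section 14.0 is the ICC of 0.2 for the Aim 1 simulation, which concerns other outcomes and is far lower. What stands is that the sponsor may choose to supply the missing assumption instead of changing the number.

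It is also fair to say that alpha is an assumption here. The figures 0.47 and 57% depend on it; the conclusion that 80% is not reached holds at each alpha level the plan uses elsewhere.

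Four stronger readings are tempting, and the documents do not support them.

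- A reader might infer that the trial's sample size is undermined. It is not: the primary outcomes are anxiety, depression, worry and rumination; the superiority criterion in Section 13.1 uses no biomarker; Sections 1.0 and 4.1 describe the biomarker work as exploring an association; and the 240 does not rest on this figure.
- A reader might link 0.36 to the IL-6 effect of g=0.36 against waitlist reported in Section 3.0. The Aim 3 paragraph makes no such link; only the numbers match.
- A reader might conclude that losses were left out of the calculation. The match with all 240 is consistent with that, but the cause cannot be known from the text.
- A reader might count three equal errors. The two Aim 1 figures are worded as at-least effects and understate sensitivity. Both would fit a sample deflated by 1.2 (96/1.2 = 80; 216/1.2 = 180), but no such factor is stated. Applied to Aim 3, it would make matters worse (144/1.2 = 120, d=0.516).

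**Conclusion.** The Aim 3 statement overstates power by about 23 percentage points at its own effect size, or equivalently understates the detectable effect (0.36 stated, 0.47 computed). This rests on a two-sample t-test with equal arms and two-sided alpha 0.05. The first two follow from the plan; the third is assumed. The error concerns a non-primary aim and changes neither enrolment nor the primary conclusion, but it is a plain misstatement in the governing document and cheap to correct. The patient and the worry and rumination figures are minor inconsistencies in the safe direction, not underpowering.

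**What to change.** In the Aim 3 power paragraph, state alpha and sidedness, then do one of two things:

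1. Restate the figure: 80% power for d=0.47 (n=144, two-sided 0.05), with 57% power at d=0.36. If another alpha is chosen, use the matching figures from the table.
2. Keep d=0.36, but define its scale and state and justify the correlation or variance reduction that supports it.

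In the Aim 1 power paragraph, either restate the two figures (patients d=0.58 with n=96; worry and rumination d=0.46 with n=216 at alpha 0.0125), or keep 0.63 and 0.50 and state the inflation allowance used. The second choice preserves any margin that was intended.

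The cost is a few edited sentences and a less favourable Aim 3 figure. Enrolment, procedures and the analysis model stay as they are.
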